The frequency of TEAEs differs with indication (i.e., TGCT, AML, and advanced malignancy), and the combination of PLX3397 with other chemotherapeutic or targeted therapies may increase the risk and/or severity of adverse findings associated with the individual agents. Individual protocols contain details for AE monitoring and dose modification and should be closely followed.

Hepatotoxicity is an important adverse drug reaction. Elevations of liver transaminases and bilirubin have been observed in studies with PLX3397, together with cases of drug-induced cholestasis. Cholestasis has been observed in the first 8 weeks and has generally resolved with treatment discontinuation, but in some patients it has been severe, with a protracted course requiring liver dialysis and, in 1 case, transplantation.

Hepatotoxicity may be fatal. One fatal case with ongoing cholestatic liver injury at the time of death has been reported. Protocol-defined dose reductions and discontinuations of PLX3397, frequent laboratory monitoring, and reporting of findings must be followed. In addition, rechallenge with PLX3397 should not be attempted without prior discussion with the Sponsor's Medical Monitor.

In uncontrolled clinical studies of single agent PLX3397 and in combination with other anti-cancer agents, bone marrow suppression with leukopenia (neutropenia and/or lymphopenia), anemia, and thrombocytopenia, either alone or with pancytopenia, has been observed. If clinically significant reduction of neutrophils, serum hemoglobin, or platelets counts is observed, the patient should be monitored closely, and protocol-defined dose modification should be followed. Standard-of-care supportive measures should be initiated, including broad spectrum antibiotics, or hematopoietic growth factors, as appropriate.

For full assessment, please refer to the latest version of the IB.

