9.3 Definitions of Dose-limiting Toxicity

Dose-limiting toxicities (DLTs) are defined as AEs that occur during Cycle 1, are classified as possibly or probably related to the study drug, and meet one of the following CTCAE v4.03 criteria below. DLTs will be evaluated for each cohort and for each dosing schedule. Toxicities that occur during Cycle 2 or later will be reviewed, and their impact on dose-escalation and dosing frequency will be assessed.

In each cohort, to maximize safety, there will be a 24-hour delay between the first subject enrolled and later subjects enrolled. .

Subjects who are considered in dose-escalation decisions are not allowed dose reductions during the DLT assessment window. Subjects who withdraw from the study prior to completing Cycle 1 for any reason other than a DLT will be replaced. Patient numbers must not be re-used.

A subject who experiences a DLT may remain in the trial and continue receiving study drug at a lower dose if the investigator deems the potential benefit outweighs the risk and that the subject is not eligible for, and/or interested in, an alternative therapy after consultation with the Medical Monitor.

Hematologic Toxicities

- Grade 4 neutropenia lasting >7 days
- Grade ≥ 3 neutropenia with fever
- Grade 4 thrombocytopenia
- Grade ≥ 3 thrombocytopenia lasting more than 7 days or associated with clinically significant bleeding
- Grade 4 anemia

Other Toxicities

- Any \geq Grade 3 (AE or laboratory) toxicity despite adequate supportive care/medical management except for the following:
 - Grade ≥ 3 nausea, vomiting, or diarrhea that resolves to Grade ≤ 2 within 72 hours, with or without medical intervention or prophylaxis because this would not be considered treatment-limiting in an oncology population
 - Grade 3 fatigue that resolves to \leq Grade 2 within 14 days because this would not be considered treatment-limiting in an oncology population
 - Grade ≥ 3 asymptomatic changes in alkaline phosphatase, hypomagnesemia, hyperglycemia, or hypophosphatemia that is felt by the investigator to be clinically insignificant
 - Grade 3 asymptomatic increases in transaminases (AST, ALT) confirmed upon repeat testing which resolves to \leq Grade 2 within <5 days
- Any other Grade ≥ 3 toxicity (except those noted above) for which the Principal Investigator or Sponsor deems further dose escalation inappropriate

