9.4 Dose Modification Guidelines and Stopping Rules

Toxicities that occur outside the DLT window will be taken into consideration when determining the RP2D. Reduction/interruption of dosing for AEs may take place at any time. [Table 22](#) summarizes the guidelines for dosage modification (including stopping rules) for PLX9486-related toxicities as well as guidelines for their management. Dose reductions for PLX9486 should occur in decrements of 200 mg per day and for PLX3397 should occur in decrements of 200 mg/day, depending on the toxicity grade, as noted in [Table 21](#). [Table 23](#) summarizes the guidelines for dosage modification (including stopping rules) for PLX3397-related toxicities (excluding liver function abnormalities) and guidelines for their management. [Table 24](#) summarizes the guidelines for PLX3397 dosage modifications (including stopping rules) for liver function abnormalities, and [Table 25](#) provides additional liver evaluations for the management of liver function abnormalities.

Dose reductions of one or both study drugs will be made based on the known toxicity of PLX3397 and on the specific toxicity of PLX9486, and will be made only after decision by the Sponsor's medical monitor in discussion with the investigator(s). The dose modification guidelines in [Table 22](#) are applicable to all parts of the study. Dose modifications of sunitinib should follow the USPI, as well as the guidance below.

If a stable combination dose of PLX9486 and PLX3397 is unattainable, dosing will be halted and a new dose configuration with a lower dose of PLX3397 (e.g., 600 mg PLX3397 and 150 mg PLX 9486) will be developed. For the combination parts of the study (Part 2b and [redacted]), if one study drug needs to be temporarily discontinued due to an adverse event, then both drugs need to be discontinued until the adverse event resolves per the dose modification guidelines. If one study drug needs to be permanently discontinued, then both study drugs must be permanently discontinued and the patient taken off-study.

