Grade 4 ALT or AST ($>20 \times \text{ULN}$)	Discontinue treatment Monitor 2x/week until resolution to Grade 2 Follow-up until resolution Grade 0–1 or baseline Check for changes to medications and for symptoms	All outcomes	Discontinue treatment; Proceed to liver evaluation as outlined in Table 25 . If clear confirmed alternate cause, restart on resolution to Grade 0–1 or baseline at 1 dose lower (reduce by one 200 mg capsule)
Any grade ALT or AST increase ^a with any bilirubin increase or signs of hypersensitivity	Discontinue treatment Monitor 2x/week until resolution to Grade 2 Follow-up until resolution Grade 0–1 or baseline Check for changes to medications and for symptoms	All outcomes	Discontinue treatment; Proceed to liver evaluation as outlined in Table 25 . If clear confirmed alternate cause, restart on resolution to Grade 0–1 or baseline at 1 dose lower (reduce by one 200 mg capsule)

ALT = alanine aminotransferase; AST = aspartate aminotransferase;

CTCAE = Common Terminology Criteria for Adverse Events; ULN = upper limit of normal

^a An increase in bilirubin is defined as all of the following: total bilirubin $>\text{ULN}$, total bilirubin $>20\%$ above baseline, and direct bilirubin $>\text{ULN}$. If all of these conditions are met, then bilirubin is considered increased and should be immediately re-checked. PLX3397 treatment should be immediately discontinued for increased bilirubin unless and until there is a clear, confirmed alternate cause.

^b If ALT, AST, or bilirubin worsens during the monitoring period, follow the applicable guidance for the worst toxicity grade.

Table 25: PLX3397 Additional Liver Evaluation

Evaluation	Comments
Increase frequency of testing liver chemistries to twice per week, including INR, and continue until liver chemistries have stabilized, and then reduce to weekly until liver chemistries return to normal or baseline.	Investigational treatment may be started after liver function tests recover to Grade 0 to 1 or baseline level, and in consultation with Medical Monitor.
Detailed history focusing on medications and substances used: alcohol, change in medication dosages, new medications added, attention to use of acetaminophen, OTC medication use, and recreational drug use. Check for change in diet or use of dietary supplements, with particular attention to dose and duration of any herbal product.	Suspect medications will be discontinued or substituted for if possible.

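### In Part 2b, liver events below the DLT threshold can end treatment in Cycle 1 without counting as DLTs, and the protocol gives conflicting rules on whether those patients are replaced or evaluable

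*Protocol*

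**What the plan says.** **When PLX3397 must stop.** The last row of Table 24 (Section 9.4) requires discontinuation for an ALT or AST increase of any grade "with any bilirubin increase or signs of hypersensitivity". Footnote a counts bilirubin as increased when total and direct bilirubin are both above ULN and total is more than 20% above baseline. It adds: "PLX3397 treatment should be immediately discontinued for increased bilirubin unless and until there is a clear, confirmed alternate cause". The row has one exit: "If clear confirmed alternate cause, restart on resolution to Grade" 0-1 or baseline, one dose lower.

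**What follows for the patient.** For the PLX3397 combination, Section 9.4 says: "If one study drug needs to be permanently discontinued, then both study drugs must be permanently discontinued and the patient taken off-study".

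**What is a DLT.** For non-hematologic toxicity, Section 9.3 and the synopsis require a possibly or probably related Cycle 1 event of at least "Grade 3 (AE or laboratory) toxicity despite adequate supportive care/medical management". Among the exceptions in Section 9.3 are "Grade 3 asymptomatic increases in transaminases (AST, ALT) confirmed upon repeat testing which resolves to" Grade 2 or lower in under 5 days, with no condition on bilirubin. The closing catch-all is also limited to Grade 3 or higher.

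**Who is replaced.** Section 9.3 says: "Subjects who withdraw from the study prior to completing Cycle 1 for any reason other than a DLT will be replaced". Later in the same section, and in the synopsis, discontinuation for Grade 2 or higher toxicity is taken out of the replacement rule and a limit of fewer than 21 of 28 days dosed is added. The same text requires a patient without a DLT to complete 28 days to be evaluable. Section 10.4 allows discretionary replacement only for withdrawals not due to toxicity or clinically significant progression.

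**The known risk.** On PLX3397, Section 5.6.1 calls hepatotoxicity an important adverse drug reaction and states: "Hepatotoxicity may be fatal". Section 5.10 notes that PLX9486 may enhance the known toxicities of PLX3397.

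**The concern.** The primary aim of Part 2b is the safety of the pair and an RP2D, and escalation runs on a 3+3 DLT count over 28 days. Table 24 has no grade floor where ALT or AST and bilirubin rise together, whereas the DLT list has a Grade 3 floor. A patient can therefore be taken off both drugs for a liver event in Cycle 1 and add nothing to the DLT numerator.

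The denominator is also unclear. Depending on which sentence a site or the Study Committee applies, the same patient is replaced, counted as having no DLT, or neither. Two cohorts with identical data could lead to different escalation decisions, and the reported DLT rate would not show how many patients were lost to liver stops.

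**Working it through.** **Step 1. Which liver events fall in the gap.** All are related Cycle 1 ALT/AST rises with a bilirubin increase and no confirmed alternate cause, so Table 24 requires discontinuation in every row. Bilirubin is assumed not to reach Grade 3, which would itself be a DLT.

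| ALT/AST grade | DLT under Section 9.3? |
|---|---|
| 1-2 | No |
| 3, asymptomatic, down to Grade 2 or lower in under 5 days | No (exempt) |
| 3, outside the exemption | Yes |
| 4 | Yes |

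The first two rows are the gap. The synopsis words the Grade 3 exemption differently (5 days or less, not restricted to asymptomatic rises), so the edge of the second row also depends on which text is used.

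**Step 2. How a patient in the gap is counted.**

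| Case | Section 9.3, withdrawal sentence | Section 9.3, evaluability paragraph, and synopsis | Section 10.4 |
|---|---|---|---|
| Grade 1, fewer than 21 days dosed | Replaced | Replaced | Outside the replacement permission |
| Grade 1, 21 to 27 days dosed | Replaced | Not replaced, but 28 days not completed: undefined | Outside the replacement permission |
| Grade 2, or exempt Grade 3 | Replaced | Not replaced, but 28 days not completed: undefined | Outside the replacement permission |

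The sources agree in no row, and no reading puts the event in the numerator.

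**Step 3. Reproduce the plan's figures.** With p the per-patient DLT probability, the 3+3 rule escalates after 0 of 3, or after 1 of 3 followed by 0 of 3:

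P(p) = (1-p)^3 + 3p(1-p)^2 × (1-p)^3

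For p = 0.10 to 0.70 in steps of 0.10 this gives 0.906, 0.709, 0.494, 0.309, 0.172, 0.082 and 0.032. Table 29 (Section 12.9.3) prints 0.91, 0.71, 0.49, 0.31, 0.17, 0.08 and 0.03. All seven agree. The table is right for events that meet the DLT definition, and only for those.

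**Step 4. Size the gap.** Let d be the probability of a DLT and q the probability of a Cycle 1 liver stop that is not a DLT, the two being mutually exclusive. The documents give neither, so both are assumptions.

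- If the liver stops counted: p = d + q.
- If the patients are replaced: p = d/(1-q), the DLT rate among those who remain evaluable.
- If the patients are kept as evaluable without a DLT: p = d.

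Example with d = 0.10 and q = 0.20: counted, p = 0.30 and P = 0.494; replaced, p = 0.10/0.80 = 0.125 and P = 0.862; kept, p = 0.10 and P = 0.906.

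| d | q | Counted | Replaced | Kept as non-DLT |
|---|---|---|---|---|
| 5% | 10% | 0.81 | 0.97 | 0.97 |
| 5% | 20% | 0.60 | 0.96 | 0.97 |
| 10% | 10% | 0.71 | 0.89 | 0.91 |
| 10% | 20% | 0.49 | 0.86 | 0.91 |
| 10% | 30% | 0.31 | 0.83 | 0.91 |
| 20% | 10% | 0.49 | 0.66 | 0.71 |
| 20% | 20% | 0.31 | 0.60 | 0.71 |

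Most of the difference lies between the first result column and the other two, so it comes from the DLT definition. Replacement against retention moves the result by at most 0.11 in this table. Retention as a non-DLT always gives the higher chance of escalating.

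**The case against.** The 3+3 count is not the only gate. Section 9.2.1.2 makes the planned Part 2b escalation conditional on the absence of related Grade 2 or higher toxicity, with no two-patient minimum, and also requires adequate safety and tolerability at the lower dose. Section 9.2.2 has the committee set the increment once two or more patients have related Grade 2 or higher toxicity. Section 9.3 sends the data of non-evaluable patients to the Study Committee, and Sections 10.1.1 and 14.4 put each escalation through sponsor and investigator review. All this stands: a related Grade 2 liver stop would not pass unseen, and the probabilities above describe the count alone, so they overstate the effect on the actual decision. But none of these provisions says how the patient is counted, and the Grade 2 provisions do not reach a Grade 1 rise that nevertheless triggers Table 24.

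A Grade 3 floor for non-hematologic DLTs is a clinical choice and is not criticised here. Section 9.4 also calls its parameters a guide, so a stop might not be strictly forced; however, Section 5.6.1 says the protocol's PLX3397 discontinuations must be followed.

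A reader might infer three stronger things that the documents do not support:

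- *Liver stops of any grade are never DLTs.* Related Cycle 1 Grade 4 rises and non-exempt Grade 3 rises are DLTs.
- *These patients are always replaced, or always permanently off study.* Replacement follows from one sentence that other text contradicts. Table 24 allows restart after a confirmed alternate cause, and the off-study rule covers only permanent stops.
- *The Part 2b results are already biased.* Table 12 shows no DLTs, and the synopsis reports no related SAE except one anemia, attributed to PLX9486 and sunitinib. No count of Cycle 1 liver discontinuations is given either way, so the effect is potential, not shown.

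**Conclusion.** The point holds as a gap and a contradiction within the protocol. Grade 1-2 ALT/AST rises, and brief asymptomatic Grade 3 rises, with raised bilirubin require PLX3397 to stop unless another cause is confirmed. They are not DLTs, and the protocol's rules on evaluability and replacement cannot all be followed for such a patient.

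Under the central illustration (10% DLTs plus 10% or 20% such stops), the count escalates with probability 0.89 or 0.86 under replacement, or 0.91 under retention as a non-DLT, against 0.71 or 0.49 if the events counted. This assumes the stated rates, mutually exclusive events, and escalation decided by the count alone. The conflict between the rules rests on the text and needs none of these assumptions. The matter should be corrected; it does not invalidate the design.

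**What to change.** Reconcile the synopsis DLT text, the two replacement statements in Section 9.3, Table 24 and Section 10.4 into one evaluability and replacement rule. It should say explicitly how a Cycle 1 discontinuation mandated for drug-related toxicity is counted when the event is not a DLT, so that the patient is not silently replaced. The two wordings of the Grade 3 transaminase exemption should be aligned at the same time.

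Do not rely on merely keeping such patients in the denominator as non-DLTs. In the central illustration that raises the chance of escalating from 0.89 or 0.86 to 0.91.

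At each escalation decision, show the Study Committee the number of patients with a DLT or a toxicity-mandated discontinuation beside the DLT count, by cohort.

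Whether the DLT definition itself should change is for the sponsor; no clinical threshold is proposed here. The cost is a short amendment to the text and one extra row in the escalation listing. The downside is that some cohorts may look less tolerable than the DLT count alone suggests.

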QTcF >500 msec or 60 msec increase from baseline verified on repeat ECG	First appearance	Interrupt study drug until resolved.	Upon recovery to QTc ≤ 500 ms (grade ≤ 2), restart at a reduced dose (at least one dose level). Permanently discontinue study drug if the QTc interval remains >500 ms and increased >60 ms from pretreatment values (after controlling cardiac risk factors for QT prolongation e.g., electrolyte abnormalities, congestive heart failure, and bradyarrhythmias) ^b .

Note: The guidelines in this table apply to all parts of the study.

^a See [Section 9.2](#) for dose levels.

^b QTc: Only one dose reduction is permitted per patient. Prior to and following treatment initiation or after dose modification of study drugs for QTc prolongation, evaluate ECG and electrolytes (including potassium, magnesium, and calcium) after 15 days and monthly thereafter or more often as clinically indicated.

Table 24: PLX3397 Dose Modification Guidelines for Liver Function Abnormalities or Bilirubin Increases

Toxicity Grade CTCAE v0.4	Initial Action	Outcome	Action
ALT or AST Grade 2 ($>3\text{--}5 \times \text{ULN}$); No increase in bilirubin ^a	Re-check ALT and AST immediately Hold study drug Monitor weekly ^b Check for changes to medications and for symptoms	Resolution to Grade 0–1 or baseline (no bilirubin increase)	Restart on resolution Grade 0–1 or baseline at 1 dose lower (reduce by one 200 mg capsule)
Grade 3 ALT or AST increase ($>5\text{--}20 \times \text{ULN}$); No increase in bilirubin ^a	Re-check ALT and AST immediately Hold study drug Monitor 2x/week ^b Check for changes to medications and for symptoms	Resolution to Grade 0–1 or baseline (no bilirubin increase) within 14 days	Restart on resolution to Grade 0–1 or baseline at 1 dose lower (reduce by one 200 mg capsule)
		ALT and AST not decreasing within 14 days of holding study drug	Proceed to liver evaluation as outlined in Table 25 . Restart only on resolution to Grade 0–1/baseline at 1 dose lower (reduce by one 200 mg capsule); For max AST or ALT $>8 \times \text{ULN}$, consult with medical monitor prior to re-start

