9.4.1 Dose Interruptions

Dose interruptions for Grade 2 toxicity for up to 1 week can be implemented at the discretion of the treating physician to manage intolerable or clinically significant toxicity. No dose reduction is required when resuming treatment.

Dose interruptions in the middle of a treatment cycle will not affect the cycle and day count on the schedule of assessments. For example, if study drug(s) is (are) held on Cycle 1 Day 10, the following day should still be called Cycle 1 Day 11. If a dose interruption occurs at the

beginning of a new cycle, then the new cycle and day count will begin when study drug is restarted. For example, if study drug is held at the Cycle 2 Day 1 visit, then the day that the patient does resume dosing will be called Cycle 2 Day 1.

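### PLX3397 liver rules disagree in two separate places: Table 24 against Section 9.4.1 for Grade 2 ALT/AST rises, and Table 24 against the Table 25 restart comment for Grade 4, bilirubin and hypersensitivity events

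*Protocol*

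**What the plan says.** All the relevant text is in Protocol Section 9.4 and its subsection 9.4.1.

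- **Table 24, Grade 2 ALT/AST without a bilirubin increase.** The drug is held, then: "Restart on resolution Grade 0–1 or baseline at 1 dose lower". No alternate cause is asked for.
- **Table 24, Grade 3 without a bilirubin increase, not decreasing within 14 days of the hold.** The patient goes to Table 25 for evaluation, and: "Restart only on resolution to Grade 0–1/baseline at 1 dose lower (reduce by one 200 mg capsule". The Medical Monitor is consulted before restart if the peak exceeded 8 times the upper limit of normal. No alternate cause is asked for.
- **Table 24, Grade 4, or any-grade rise with a bilirubin increase or signs of hypersensitivity.** Treatment is discontinued and the patient goes to Table 25. Restart is conditional: "If clear confirmed alternate cause, restart on resolution to Grade 0–1 or baseline at 1 dose lower (reduce by one 200 mg capsule". For bilirubin, footnote a adds: "PLX3397 treatment should be immediately discontinued for increased bilirubin unless and until there is a clear, confirmed alternate cause".
- **Table 25, comment beside the first evaluation row.** "Investigational treatment may be started after liver function tests recover to Grade 0 to 1 or baseline level, and in consultation with Medical Monitor".
- **Section 9.4.1.** Interruptions of up to one week for Grade 2 toxicity are at the treating physician's discretion, and: "No dose reduction is required when resuming treatment". The section names no exception.

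**The concern.** A site handling a liver event under PLX3397 can find two instructions in the same part of the protocol that lead to different actions. For a Grade 2 rise they differ on whether a hold is required and on the dose at restart. For a Grade 4 event, or one with bilirubin or hypersensitivity features, they differ on whether a patient who recovers with no alternate cause found may restart at all.

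This matters for three reasons.

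- **Patient safety.** Section 5.6.1 calls hepatotoxicity an important reaction to PLX3397. Across the wider programme it reports severe cholestasis, one transplantation and one death with ongoing cholestatic liver injury.
- **The primary endpoints of Part 2b** are the RP2D of the combination and its safety and tolerability. Dose intensity, re-challenge and discontinuation all depend on which passage a site follows. Section 9.4 also takes a patient off both drugs and off study if one drug is permanently stopped.
- **Dose-escalation data.** Section 9.3 does not allow dose reductions in the DLT window for patients counted in escalation decisions. A Grade 2 rise in Cycle 1 is met with a reduction under Table 24, while Section 9.4.1 does not require one. The choice of passage could therefore bear on whose data inform escalation.

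**Working it through.** No computed figure is involved, so the check sets the passages side by side for each type of event.

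| Liver event | Table 24 | Other passage | Result |
|---|---|---|---|
| Grade 2, no bilirubin increase, hold of up to 1 week | Hold; restart on recovery, one dose lower | Section 9.4.1: hold discretionary; no reduction required | Direct disagreement on the hold and on the dose |
| Grade 2, no bilirubin increase, hold longer than 1 week | As above | Outside Section 9.4.1 | One instruction |
| Grade 3, no bilirubin increase, resolving within 14 days | Restart one dose lower; not sent to Table 25 | None | One instruction |
| Grade 3, no bilirubin increase, not decreasing within 14 days | Table 25 evaluation; restart one dose lower; consult if above 8 times ULN | Table 25: restart on recovery with consultation; dose not mentioned | Table 25 silent on dose; scope of consultation differs; neither asks for an alternate cause |
| Grade 4, or any grade with bilirubin increase or hypersensitivity signs | Discontinue; Table 25 evaluation; restart only with confirmed alternate cause, one dose lower | Table 25: restart on recovery with consultation; cause and dose not mentioned | Different outcome for a patient who recovers with no alternate cause, if Table 25 is read alone |

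The next question is whether any passage says which text governs.

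1. The introduction to Section 9.4 gives PLX3397 liver dose modifications and stopping rules to Table 24, and describes Table 25 as supplying further liver evaluations. This favours Table 24.
2. A later paragraph of Section 9.4, just before Table 23, lists Tables 23, 24 and 25 together as the guidelines for reducing or interrupting PLX3397. Table 25 is thus also cited as dosing guidance, and its comment is in substance a restart statement. The paragraph does not rank Table 24 against Table 25, and it too allows discretionary interruptions.
3. Section 9.4 says its parameters are guidance that does not override the treating physician. Section 5.6.1 says protocol-defined reductions and discontinuations of PLX3397 have to be followed. These pull in different directions and neither ranks the three passages.
4. Section 9.4.1 is general and Table 24 is liver-specific, but the protocol does not say that the specific rule prevails.

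Two separate inconsistencies remain, the first and last rows of the table, with a lesser gap for the slow-resolving Grade 3 case.

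**The case against.** The strongest reply is that the passages can be read together. Table 25 is titled as an evaluation table. Its restart sentence sits in a comments column beside a test-frequency row, and for dosing purposes patients reach it from Table 24 cells that state their own restart conditions. On that reading, the comment is a minimum condition common to all referrals, and Table 24's conditions on cause and dose still apply. Section 9.4.1, likewise, is a general discretionary provision that yields to a liver-specific table. Central control is also substantial: Section 9.4 requires Medical Monitor involvement in dose changes, Section 5.6.1 requires prior discussion before rechallenge, and Table 25 requires consultation.

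Much of this stands. It shows that Table 25 is silent on cause and dose and does not state the reverse of Table 24. It also makes unsupervised re-exposure unlikely. It does not supply a rule of precedence, and the Medical Monitor has no single restart criterion to apply.

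Three stronger readings are tempting, and the document does not support them.

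- **That one and the same liver event is treated in opposite ways by all three passages.** The alternate-cause condition does not appear in the Grade 2 row, which is where Section 9.4.1 conflicts with Table 24. The two conflicts concern different events.
- **That one site may restart at full dose after a Grade 4 or bilirubin event while another must stop, both fully within protocol.** A full-dose restart would breach the text of the Table 24 row, and Table 25 itself requires consultation.
- **That every rise of Grade 2 or worse is affected.** An assumed 10% to 20% of the approximate ceiling of 30 patients in Part 2b would give 0.10 × 30 = 3 to 0.20 × 30 = 6 patients. The protocol gives no such rate, and the count wrongly includes Grade 3 events that resolve within 14 days and Grade 2 holds beyond one week.

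The transplantation and the death come from the wider PLX3397 programme. In this study, the synopsis reports one treatment-related SAE (anemia) and no treatment-related deaths as of 26 April 2019.

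**Conclusion.** The point holds as two distinct inconsistencies in the PLX3397 liver rules.

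1. For Grade 2 ALT/AST without a bilirubin increase, Table 24 and Section 9.4.1 disagree on the hold and on the restart dose. This is the more direct conflict. It is limited to holds of up to one week.
2. For Grade 4 events, and any-grade rises with a bilirubin increase or hypersensitivity signs, Table 24 sets conditions on cause and dose (footnote a repeats the cause condition for bilirubin) that the Table 25 comment omits. For Grade 3 rises not decreasing within 14 days, the comment omits only the reduced dose.

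The number of patients affected cannot be derived, because no liver event rate is given. The conclusion assumes that Table 25 can be read as dosing guidance, as the paragraph before Table 23 allows, and that no rule of precedence stands elsewhere in the protocol; none was found. This is an error of wording with a bearing on patient safety. It needs correcting, but it does not undermine the design or the planned analysis. No view is taken on which clinical rule is right.

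**What to change.** The sponsor should reconcile Table 24, Table 25 and Section 9.4.1 so that each type of PLX3397 liver event has one restart instruction. Two edits would do it:

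- Have the Table 25 comment refer to the applicable Table 24 row, or amend Table 24 if the Table 25 wording is what was intended.
- State in Section 9.4.1 whether PLX3397 liver events are excepted from the general Grade 2 provision, and align the Grade 2 row of Table 24 with the answer.

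A sentence in Section 9.4 naming which passage prevails would close any remaining gap. The clinical content is for the sponsor to decide. The cost is one table comment, one or two sentences and a notice to sites. Sample size, endpoints and planned analyses do not change.
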